14.1.4 Visit 4 (group 1 to 4 only)

The activities and assessments to be performed at Visit 4 are outlined below. For details on the timing of each assessment, refer to Table 2.

The following activities and assessments will be performed:

- Review of diary since the previous visit.
- AE collection.
- Recording of concomitant medications.
- Recording of vital signs (heart rate and blood pressure).
- 12-lead ECG.
- Physical examination.
- Urine sampling of urinalysis parameters.
- Blood sampling for assessment of haematology and clinical chemistry parameters. Fasting is not required.
- Nasal swab for nasal IgA analysis.
- Blood sampling for immunology analyses.

14.1.5 Safety follow-up (telephone calls)

AEs of special interest and SAEs will be collected during 6 months after the last vaccination through telephone calls approximately every 8th week ± 7 days following the last visit to the clinic for a total of 3 occasions

The following will be collected:

- Potential immune-mediated diseases (pIMDs). pIMDs are a subset of AEs that include both clearly autoimmune diseases and also other inflammatory and/or neurologic disorders which may or may not have an autoimmune aetiology.
- SAEs

The questions to be asked are:

- Have you, since the last contact, visited any healthcare facility or hospital? If yes, please describe the reason for the visit, the assessment given and what treatment you received.
- Have you, since the last contact, experienced any worsening in a chronic disease that you are diagnosed with? If yes, please describe the symptoms.
- Are you pregnant? If yes, which week?

The information will be collected in the eCRF. The questions translated into Swedish are found in Appendix 4.

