Administration site reactions will be collected at the clinic during 2 hours of observation after each study drug administration. In previous studies with Endocine products such reactions, if occurring, were transient and in the vast majority of cases disappeared within this time period. Possible later local and systemic reactions will be collected over 10 days using a diary. In accordance with the guidelines on influenza vaccines and adjuvanted vaccines a long-term safety follow-up for 6 months after the last vaccination is included to detect any potential late occurring immune-mediated diseases (IMDs) that may be associated with the vaccination.

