10.1.1 Primary endpoints

- Type and incidence of AEs and SAEs from the time of first study drug administration (Visit 2) until the last visit to the clinic (Visit 4 for group 1 to 4 and Visit 3 for group 5 to 6).
- Type and incidence of SAEs and AEs of special interest during the 6 months safety follow-up.
- Frequency and severity of administration-site reactions as assessed by an independent evaluator with help from study subject before study drug administration and 15 minutes and 120 minutes after study drug administration. Administration-site reactions to be recorded are swelling, redness, pain and pruritus in the administration area (nose or arm). Reactions are classified as none, mild, moderate or severe. The administration-site reactions pain and pruritus will also be recorded by the subject in an electronic diary for 10 days starting in the evening the day after each treatment and classified as none, mild, moderate or severe.
- Frequency of solicited AEs. The subjects will record the occurrence of solicited AEs in an electronic diary for 10 days after study drug administration. Solicited AE include runny nose, nasal congestion, sneezing, fever (i.e., temperature >38°C), chills, sweating, headache, tiredness, muscle aches, joint pain, cough, sore throat, nausea.
- Frequency of clinically significant changes in ECG, vital signs, physical examination findings and laboratory variables from baseline to the last visit to the clinic.

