15.3.2 Adverse event questioning and recording

The Investigator is to record all directly observed AEs and all AEs spontaneously reported by the subject in the subject's personal records (source data) and in the eCRFs using concise medical diagnostic terminology.

The occurrence of an AE may come to the attention of personnel during a site visit or during interview of a subject presenting for medical care. The question asked will be "Have you had any health problems since your last evaluation?". AEs may also be identified upon review by a monitor who is scrutinising relevant source data.

All AEs must be graded for:

- Seriousness (Section 15.3.3)
- Intensity (Section 15.3.7.1)
- Causality (possible relationship) to IMP (15.3.7.2)

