15.3.6 Definition of adverse events of special interest

Adverse events of special interest include pIMDs occurring during the 6 months safety follow-up period (Section 14.1.5 and 15.3.11).

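### The 6-month telephone script can elicit a new-onset immune-mediated disease only if the subject has already had healthcare contact, so the recorded incidence of a primary endpoint may be too low

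*Combined protocol and SAP*

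**What the plan says.** Section 9.5 gives the purpose of the 6-month follow-up: it "is included to detect any potential late occurring immune-mediated diseases (IMDs) that may be associated with the vaccination". Section 10.1.1 makes the result a primary endpoint: "Type and incidence of SAEs and AEs of special interest during the 6 months safety follow-up". Section 15.3.6 ties the two together: "Adverse events of special interest include pIMDs occurring during the 6 months safety follow-up period". Section 14.1.5 defines potential immune-mediated diseases (pIMDs) broadly, as autoimmune diseases plus "other inflammatory and/or neurologic disorders which may or may not have an autoimmune aetiology".

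Section 14.1.5 also lists the questions to be put in the calls:

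- "Have you, since the last contact, visited any healthcare facility or hospital", with a request for the reason, the assessment and the treatment if the answer is yes;
- "Have you, since the last contact, experienced any worsening in a chronic disease that you are diagnosed with", with a request for the symptoms;
- whether the subject is pregnant.

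Appendix 4 is described only as the Swedish translation of these questions. Section 15.3.11 repeats what is to be collected, refers back to 14.1.5 and adds no prompt.

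The protocol does contain an open question, in section 15.3.2: "Have you had any health problems since your last evaluation". It is described for site visits and for subjects presenting for medical care, and it is not in the call script. Under section 15.3.12, general AE collection stops at the last clinic visit; after that only SAEs and AEs of special interest (AESIs) are documented.

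**The concern.** After the last clinic visit the three calls are the only scheduled contact, so the script is in effect the measuring instrument for the follow-up endpoint. The subjects are healthy volunteers aged 18 to 39 with no serious illness (12.4). Severe or progressive neurologic disease, seizure disorder and immunodeficiency are excluded (12.5). An immune-mediated disease in this population will mostly be new onset. The question on worsening chronic disease applies to few of them and by its wording cannot reveal a new disease. That leaves the question on healthcare contact, which depends on the subject having sought care.

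Safety is analysed descriptively (18.5.2), so a low or zero AESI count will be read at face value. If some cases were never elicited, that count would look more reassuring than it should.

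**Working it through.** **Step 1. Can each scripted question reveal a new-onset pIMD?**

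| Source | What it covers | New-onset pIMD with healthcare contact | New-onset pIMD without healthcare contact |
|---|---|---|---|
| 14.1.5, question 1 | Any healthcare visit, and its reason | Elicited | Not elicited |
| 14.1.5, question 2 | Worsening of a diagnosed chronic disease | Not elicited | Not elicited |
| 14.1.5, question 3 | Pregnancy | Not elicited | Not elicited |
| 15.3.2, open question | Any health problem | Not in the call script | Not in the call script |

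One route remains, through question 1. No other section supplies a new-symptom question for the calls.

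**Step 2. Which part of the 6 months depends on the script?**

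- Groups 1 to 4 (Table 1): calls on Days 81, 141 and 201, with dose 2 on Day 21. Days after the last vaccination: 81 − 21 = 60, 141 − 21 = 120, 201 − 21 = 180. With dose 2 on Day 28, the last day of its window, these become 53, 113 and 173.
- Groups 5 and 6 (Table 3): calls on Days 60, 120 and 180, with the only dose on Day 0, so again 60, 120 and 180.
- The last clinic visit is at least 3 weeks after the last dose (footnote 1 to Tables 1 and 3). It includes AE collection (14.1.3.2, 14.1.4) and a physical examination covering the neurological system (15.7). At least the first 21 of the 180 days are therefore covered by open questioning.
- At most 180 − 21 = 159 days, or 159/180 = 88% of the period, depend on the call script alone.

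**Step 3. Size, as illustration only.** The one stated figure used is the sample size, and it reproduces: 3 × 36 + 3 × 18 = 162. Section 18.2 states that there was no power calculation. The documents give no pIMD rate and no capture rate, so every capture rate c below is an assumption.

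With zero events in n subjects, the upper end of the exact two-sided 95% interval is 1 − 0.025^(1/n). If only a fraction c of cases is captured, the recorded rate is c times the true rate, so the limit on the true rate is that figure divided by c.

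| Subjects | c = 1 | c = 0.9 | c = 0.5 |
|---|---|---|---|
| Both Endocine groups, n = 36 + 36 = 72 | 4.99% | 5.5% | 10.0% |
| One Endocine group, n = 36 | 9.74% | 10.8% | 19.5% |

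The one-sided 95% bound, 1 − 0.05^(1/n), is 4.1% for 72 and 8.0% for 36 at full capture, and 8.2% and 16.0% at c = 0.5. The convention changes the numbers but not the pattern.

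The chance of recording at least one event in 72 subjects at an assumed true rate of 1% is 1 − (1 − 0.01c)^72. This is 51.5% at c = 1, 41.8% at c = 0.75 and 30.3% at c = 0.5.

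These figures apply c to all cases over the whole follow-up. Step 2 shows that the first weeks are better covered, so this simplification overstates the loss for any given c.

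**The case against.** The strongest reply is that the endpoint counts diseases, not symptoms. A symptom that no clinician has assessed is not yet a pIMD, and question 1 asks openly about the reason for and result of any healthcare visit, so it reaches any new disease that has been assessed. This stands in part. A reported symptom would need work-up before it counted, but a disease that has begun and not yet been assessed is what a follow-up for late events should bring forward.

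Other points limit the concern:

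- A reader might infer that new-onset cases are simply missed. The documents do not support that. Someone with symptoms at the first call who seeks care later can be picked up at the second or third. Subjects may also volunteer symptoms. Hospitalised events, which include many SAEs, fall under question 1.
- A reader might infer a bias between groups. None is shown. All groups get the same script, and groups 1 to 4 are blinded as far as possible (13.10). Different care-seeking in the open-label groups 5 and 6 is conceivable but speculative.
- A reader might take the discussion of narcolepsy in section 9.6 as evidence of a specific expected signal. That section attributes the finding to one pandemic vaccine, reports no increase with seasonal vaccination in Sweden in 2010-2011, and concludes that no increased risk is expected here.
- Even with perfect capture, 72 subjects without an event cannot exclude a true rate of about 4% to 5%. Sample size is the main limit on what a zero count can show, and no inferential safety claim is planned.
- Ending general AE collection at the last clinic visit is a deliberate choice, and an open question asked over a winter will bring in colds and similar reports.

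These points reduce the weight of the finding. None supplies the absent question.

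**Conclusion.** The gap is real but bounded. As written, the script can elicit a new-onset pIMD only through healthcare contact that has already taken place. New-onset disease that arises after the last clinic visit and leads to no healthcare contact by the last call may not be elicited, and other cases may be detected late. The direction is towards a lower recorded AESI incidence in every group, on a primary endpoint.

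The amount cannot be computed from the documents. The limits under 50% to 90% capture show only how such a loss would carry through to a zero count; they are not an estimate of it. The conclusion assumes that callers keep to the listed questions and that Appendix 4, whose text is not available here, is the plain translation that section 14.1.5 describes. It is a cheap improvement in ascertainment, not a flaw that invalidates the endpoint.

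**What to change.** In section 14.1.5 and Appendix 4, add one question to each call about new illness or symptoms since the last contact. It can be the open question of section 15.3.2 reworded for the calls, or a short prompt for new neurological, autoimmune or inflammatory symptoms. Keep the three existing questions. State that only SAEs and events that the investigator assesses as pIMDs are recorded from the answers, so that the scope set in section 15.3.12 is unchanged. Section 15.3.11 already refers to 14.1.5 and needs no new text.

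The cost is one extra question in three calls already planned, a numbered protocol amendment under section 19.4, and triage of some reports that turn out not to be AESIs. No visit, sample or call is added. The targeted prompt would bring in fewer irrelevant reports than the open question, but it covers less.

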14.2 EVENT DESCRIPTIONS

14.2.1 Screening and informed consent

The procedures for screening and obtaining informed consent are described in Section 12.

14.2.2 Eligibility criteria

Eligibility criteria should be checked during screening as detailed in Section 12.4 and 12.5. On dosing days, eligibility will be re-assessed based on the continued eligibility criteria detailed in Section 12.6.

14.2.3 Demography

The following demographic data will be recorded: initials, gender, birth date and ethnic origin (Caucasian, Asian or Pacific Islander, African descent, Mixed/multi-racial, or other). Full information about the subject's social security number (personnummer) and name is to remain confidential in the records of the respective Investigator.

14.2.4 Weight and height

Weight and height will be measured without shoes at screening. BMI will be calculated from the height and weight recorded and will be rounded to one decimal.

14.2.5 Medical history

Medical history should be obtained by interview and include descriptions of all relevant diseases prior to screening as judged by the Investigator.

Pre-dose events occurring between the signing of ICF and first dose will also be registered in the medical history log of the CRF.

14.2.6 Prior and concomitant medications

Medication history (prior medications) is needed for 3 months prior to screening. Prescription medications, OTC medications, and herbal products should be asked for.

Any medication used from screening until the last clinical visit (Visit 4 for subjects in group 1 to 4 and Visit 3 for subjects in group 5 and 6) will be recorded in the eCRF.

The Investigator or designee should assess changes in concomitant medications throughout the study by asking the subject at each visit. Any changes reported by the subject should be recorded in the eCRF.

Medications will be coded according to the WHO Anatomic Therapeutic Chemical classification system (ATC) classification system.

14.2.7 HIV and Hepatitis B/C

Subjects will be tested for HIV (standard HIV antibody test) and hepatitis B (HBsAg and anti-HBc) and hepatitis C (anti-HCV) prior to inclusion in the study. Any positive result at screening will exclude the subject from participating in the study.

14.2.8 Pregnancy test

All females will do a pregnancy test (urine dipstick) at screening and prior to each dosing occasion.

14.2.9 Urine drug screen

Subjects will be screened for drugs of abuse at screening using a urine dipstick. The following substances will be included in the screen panel:

- Cocaine (COC)
- Amphetamine (AMP)
- Marijuana (THC)
- Methadone (MTD)
- Morphine (MOP)
- Benzodiazepines (BZO)
- Buprenorphine (BUP)

Additional drug screens may be performed during the study at the discretion of the Investigator.

15. SAFETY ASSESSMENTS

Safety will be assessed by recording pre-defined local administration site reactions, frequency and severity of AEs, routine safety laboratory parameters, vital signs, 12-lead ECG and physical examination. The timing of assessments is shown in Table 1 to Table 4.

15.1 LOCAL TOLERABILITY ASSESSMENTS

The administration area (nasal cavity for group 1 to 4 and group 6 and upper arm for group 5) will be inspected by an independent evaluator (i.e. a person different from the one doing the administration), pre-dose and at 15 and 120 minutes post-dose to record the presence or absence of swelling and redness (none, mild, moderate or severe). At the same time points, each subject will assess presence or absence of pain and pruritus in the administration area (none, mild, moderate or severe as defined in Section 15.3.7.1). The independent evaluator will thus be blinded for all groups receiving intranasal vaccination (i.e. all test products, saline and [REDACTED]).

Local tolerability reactions classified as moderate or severe will be reported as AEs.

For all inspections, the same type of lamps will be used at both sites. To facilitate the investigation, nostrils will be slightly widened using a nose speculum.

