15.2 SUBJECT DIARY FOR ASSESSMENT OF LOCAL TOLERABILITY AND SOLICITED AEs

The subjects will be provided with an electronic diary and will be asked to record the presence of any administration site reactions (pain or pruritus) for 10 days starting in the evening the day after each treatment.

In addition, the subjects will be asked to record the occurrence of solicited AEs (fever [temperature >38°C], chills, sweating, tiredness, headache, muscle aches (not associated with the administration area), joint pain (not associated with the administration area), runny nose, nasal congestion, sneezing, cough, sore throat and nausea for 10 days starting in the evening the day after each treatment.

All reactions will be classified as none, mild, moderate or severe by the subjects. The duration of each reaction (hours) will also be recorded. Reactions classified as moderate or severe will be reported as AEs.

The diary will also contain a question as to whether the subject has taken any antipyretic medication or any other type of medication to treat the recorded symptoms. Any medication taken will be recorded as a concomitant medication.

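### Solicited recording of arm swelling and redness in Group 5 stops at 120 minutes, so later reactions to the injection may be under-counted in the site-reaction tables

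*Combined protocol and SAP*

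**What the plan says.** Section 10.1.1 sets the endpoint: "Administration-site reactions to be recorded are swelling, redness, pain and pruritus in the administration area (nose or arm"). It places all four at the pre-dose, 15-minute and 120-minute assessments, and adds the diary for pain and pruritus only.

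Section 15.1 gives the inspection times: "pre-dose and at 15 and 120 minutes post-dose to record the presence or absence of swelling and redness (none, mild, moderate or severe"). The arm follows the same schedule as the nose ("upper arm for group 5) will be inspected by an independent evaluator"). Table 3 lists no site inspection for Group 5 after Visit 2.

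Section 15.2 asks subjects to "record the presence of any administration site reactions (pain or pruritus) for 10 days starting in the evening the day after each treatment".

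Section 9.5 gives the reason for the 2-hour window: "In previous studies with Endocine products such reactions, if occurring, were transient and in the vast majority of cases disappeared within this time period". It then says: "Possible later local and systemic reactions will be collected over 10 days using a diary".

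For reporting, Section 18.5.2.2 builds the site-reaction tables from the dosing-visit evaluations (Visit 2 only for Group 5). Section 18.5.2.3 adds the diary's pain and pruritus.

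**The concern.** The evidence offered for stopping at 2 hours comes from products containing Endocine. Group 5 receives a split vaccine by intramuscular injection with no Endocine, and nothing in the documents says that its local reactions appear or resolve on the same schedule. The diary is the plan's stated means of catching later local reactions, but it has no item for two of the four signs. Its muscle-ache and joint-pain items exclude the administration area, so they cannot stand in for those signs.

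At stake is the meaning of one part of the primary endpoint in one comparator arm. Section 9.5 says both comparators were chosen partly for comparing safety and tolerability. A Group 5 frequency of arm swelling or redness would be a 2-hour frequency, and a reader could take it for the frequency over the whole reporting period.

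**Working it through.** **Plan's own figure.** 3 × 36 + 3 × 18 = 108 + 54 = 162, as stated in Section 18.2, so Group 5 has 162 × 1/9 = 18 subjects. The plan gives no power, margin or test for safety; Section 18.5.2 compares incidences descriptively.

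**What is captured for the arm, by time**

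| Period after injection | Pain, pruritus | Swelling, redness |
|---|---|---|
| 15 and 120 min | Graded (15.1) | Graded (15.1) |
| Leaving the clinic to the evening of Day 1 | Nothing solicited | Nothing solicited |
| Next 10 days | Diary, graded (15.2) | Nothing solicited |
| Visit 3, Day 21 to 28 | Open AE question, diary review | Open AE question, skin examination |

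The length of the second row is not stated. Assume dosing between 08:00 and 16:00 and a first diary entry between 18:00 and 21:00 the next day. The gap is then 24 + entry hour − (dosing hour + 2). The shortest is 24 + 18 − 18 = 24 h and the longest is 24 + 21 − 10 = 35 h.

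**Possible under-count.** Let p be the true incidence of arm swelling or redness and f the share of reactors in whom it is seen by 120 minutes. Neither is in the documents, so both are assumptions. Expected cases in the site-reaction table are 18 × p × f, and expected cases missed are 18 × p × (1 − f).

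| p (expected reactors) | f = 0.25, seen / missed | f = 0.50 | f = 0.75 | f = 1.00 |
|---|---|---|---|---|
| 0.10 (1.8) | 0.45 / 1.35 | 0.9 / 0.9 | 1.35 / 0.45 | 1.8 / 0 |
| 0.20 (3.6) | 0.9 / 2.7 | 1.8 / 1.8 | 2.7 / 0.9 | 3.6 / 0 |
| 0.30 (5.4) | 1.35 / 4.05 | 2.7 / 2.7 | 4.05 / 1.35 | 5.4 / 0 |

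The chance that the table shows no case at all is (1 − p × f)^18. At p = 0.20 and f = 0.25 this is 0.95^18 = 0.397. With full capture it is 0.80^18 = 0.018.

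**Direction against the nasal groups.** Assume a true incidence of 20% in both nose and arm. The apparent nasal excess is 0.20 × f(nose) − 0.20 × f(arm):

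- f(nose) = 0.90, f(arm) = 0.25: 0.18 − 0.05 = +13 points.
- Equal shares: 0.
- f(nose) = 0.50, f(arm) = 0.90: 0.10 − 0.18 = −8 points.

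The sign depends on relative onset, which the documents do not give.

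**Precision.** With 18 subjects the exact 95% interval is 0 to 18.5% for 0/18 and 1.4 to 34.7% for 2/18.

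**The case against.** The strongest reply has four parts.

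*The schedule is even-handed.* Nose and arm are inspected at the same times on the same scale, and no group has a diary item for swelling or redness. This stands. A reader might infer that the comparison is biased in the injection's favour, but that requires arm reactions to appear later than nasal ones, and the documents are silent on onset after the intramuscular product. A reader might also treat the diary's congestion and runny nose as a 10-day nasal counterpart that the arm lacks. Those items are put to every subject and summarised as solicited AEs, apart from site reactions, so the documents do not give them that role.

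*Late reactions are not lost.* Subjects are asked "Have you had any health problems since your last evaluation", AE collection runs to Visit 3 (Section 15.3.12), and the examination at that visit covers skin (Section 15.7). This stands in part. It would be wrong to say that late reactions go unrecorded. But the question is open and comes three to four weeks after the injection, a transient sign would have gone by then, and whatever is reported is tabulated as an AE by preferred term under Section 18.5.2.1.

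*The endpoint is not self-contradictory.* Section 10.1.1 itself limits the diary to pain and pruritus, and Section 9.5 does not promise all four signs. This is correct. The gap lies between the general intention in Section 9.5 and the items chosen to deliver it.

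*Little depends on it.* Section 9.5.1 names local tolerability as a reason for the intranasal comparator, not the injection. The sample sizes were weighted for Endocine against no Endocine, which Group 5 does not touch. Group 5 is 18 open-label subjects compared descriptively. This limits the importance of the point but does not remove the gap.

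**Conclusion.** The point holds in a limited form. Solicited assessment of swelling and redness ends at 120 minutes in all groups, on a rationale drawn only from Endocine products. For Group 5, later arm swelling or redness depends on unsolicited reporting up to Visit 3 and stays out of the site-reaction tables, so its frequency there may be under-counted. Over the assumed range (true incidence 10 to 30%, 25 to 100% visible by 120 minutes), the expected shortfall is between 0 and 4.05 of 18 subjects, at most 0.30 × 0.75 = 22.5 percentage points. The documents do not place the trial within that range, and they settle neither the size nor the direction of any effect on the comparison with the nasal groups. Two of the four site reactions in one comparator arm are affected. Arm pain and pruritus are followed in the diary, and the Endocine contrasts are untouched. It is worth correcting because it concerns a primary endpoint and the remedy is cheap.

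**What to change.** Add injection-site redness and swelling (none, mild, moderate, severe) to the Group 5 electronic diary in Section 15.2, for the same 10 days as pain and pruritus. Have the first entry also cover the time since leaving the clinic on Day 0. Without that, a reaction that appears on the evening of injection and has cleared before the diary opens would still be missed. Carry the change into Sections 10.1.1 and 18.5.2.3.

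Label the evaluator's swelling and redness table as *within 120 minutes* for all groups. Report the Group 5 diary result in its own table, without pooling it with the evaluator's grades.

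The cost is two diary items for 18 subjects who can see their own arm, and one table. Group 5 is open label, so blinding is unaffected. The drawbacks are that the new items are self-assessed, exist for the arm only, describe just 18 subjects, and rely on about a day's recall at the first entry. Under Section 15.2, reactions graded moderate or severe would also be reported as AEs, which the report should note when Group 5 AE counts are compared with those of other groups.

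If the diary cannot be changed, the minimum is the table label and a statement that later arm swelling and redness in Group 5 rest on unsolicited reporting.

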9.5 RATIONALE FOR THE STUDY DESIGN, DOSES AND CONTROL GROUPS

Immunose FLU with 2 different concentrations of Endocine will be investigated to assess the influence of adjuvant concentration on the response parameters, whereas the antigen dose will be kept constant according to standard practice for influenza vaccinations. The inactive control group (saline) is included for an enhanced interpretation of safety data through control for placebo effects, and for the analysis of immune responses through control for background antibody levels. The comparators to Immunose FLU; ██████████ for intranasal administration and ██████████ for intramuscular injection of antigen have been selected to compare the safety and tolerability and the overall immune response.

Immunose FLU will be administered at 2 occasions with a 3-week interval to maximize the magnitude of the immune response as indicated by non-clinical data. Influenza antigen without adjuvant and saline alone will also be administered nasally at two occasions. ██████████ and ██████████ will be administered at one occasion according to the prescribing information.

Endocine will be tested at the concentrations 1% and 2% in two different treatment groups. In a previous study with nasal influenza vaccination, Endocine was evaluated with concentrations ranging from 0.5% to 2% (report EV 2011-08, EUR-001). Local tolerability symptoms were more commonly reported following vaccination with Endocine compared to vaccination without Endocine with a slightly higher incidence of reactions following administration of 2% compared to 0.5% and 1%. Symptoms were rapidly reversible and there were no safety concerns for any treatment group. In the present study the dose-response for Endocine versus safety variables and immune response will be evaluated, and the dose steps 1% and 2% are considered adequate.

The immunology variables to be investigated in the study have been selected to represent both systemic and local immune responses, which both might be indicative of the protective efficacy in later studies.

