18.5.2.2 Local tolerability assessments

The administration-site reactions swelling, redness, pain and pruritus in the nose or arm will be classified as none, mild, moderate or severe. The evaluations will be performed at study visits 2 and 3 for group 1 to 4 and visit 2 for group 5 and 6, both before and after dose. The results will be summarised graphically and in frequency tables.

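### In-clinic pain and pruritus are rated only as they stand at 15 and 120 minutes, so brief reactions within the 2-hour observation can be tabulated as none

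*Combined protocol and SAP*

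**What the plan says.** The rationale in section 9.5 describes collection over a period: "Administration site reactions will be collected at the clinic during 2 hours of observation after each study drug administration". It adds that in previous studies with Endocine products "such reactions, if occurring, were transient and in the vast majority of cases disappeared within this time period". Of the earlier nasal influenza study it says: "Symptoms were rapidly reversible and there were no safety concerns for any treatment group". No onset time or duration in minutes is given anywhere.

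The measurement is set at points in time. The primary endpoint in section 10.1.1 (and the synopsis) places the assessment "before study drug administration and 15 minutes and 120 minutes after study drug administration". Section 15.1 has the independent evaluator inspect the site "pre-dose and at 15 and 120 minutes post-dose to record the presence or absence of swelling and redness", and for the subject-rated symptoms states: "At the same time points, each subject will assess presence or absence of pain and pruritus in the administration area". Tables 2 and 4 allow +5 minutes on the first check and ±5 minutes on the second. No wording asks for the worst symptom since dosing or since the previous check.

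For the analysis, section 18.5.2.2 says of these ratings: "The results will be summarised graphically and in frequency tables".

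The electronic diary (section 15.2) opens in the evening of the day after treatment. It also records how long each reaction lasted; the in-clinic ratings do not.

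**The concern.** Current-status ratings at two times give point prevalence, which depends on how many subjects react and on how long the reaction lasts. The rationale speaks of reactions over the whole 2 hours. With short-lived reactions these two quantities can differ.

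Nasal stinging from minute 0 to minute 12, or itch from minute 25 to minute 100, would be absent at both checks. Under section 18.5.2.2 that subject would count as having had no pain or pruritus on the day. The diary starts too late to correct this.

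Administration-site reactions are part of the primary endpoint. Section 18.2 names the effect of Endocine on tolerability, against antigen without it, as a key objective and the reason groups 1 to 3 are larger. Absolute frequencies may be understated in every group. Group comparisons may also be affected if reaction duration differs by formulation.

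**Working it through.** **Inputs from the documents.** Checks at 15 minutes (up to 20 with the window) and 120 minutes (sections 10.1.1 and 15.1, Tables 2 and 4). Reactions mostly gone within 2 hours (section 9.5). The plan states no rate, power or duration for this endpoint, so there is no figure to reproduce.

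**Assumptions, because the documents are silent.** Onset times as stated below. Duration exponential with mean m minutes, m from 10 to 60.

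**Step 1. Onset at dosing.** The probability of being present at time t is exp(−t/m). Any such reaction present at 120 minutes is also present at 15, so the first check determines capture.

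| Mean m (min) | Present at 15: exp(−15/m) | Present at 20: exp(−20/m) | Gone by 120: 1 − exp(−120/m) |
|---|---|---|---|
| 10 | 22% | 14% | over 99% |
| 15 | 37% | 26% | over 99% |
| 20 | 47% | 37% | over 99% |
| 30 | 61% | 51% | 98% |
| 45 | 72% | 64% | 93% |
| 60 | 78% | 72% | 86% |

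Capture at 15 minutes equals one half when m = 15/ln 2 = 21.6 minutes. The last column shows that means across this range, including 45 and 60 minutes, are compatible with most reactions having gone within 2 hours. Section 9.5 therefore does not say which row applies.

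**Step 2. Onset spread evenly between the checks (15 to 120 minutes).** The probability of being present at 120 minutes is (m/105) × (1 − exp(−105/m)).

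- m = 10: 0.0952 × 1.000 = 10%
- m = 20: 0.1905 × 0.995 = 19%
- m = 30: 0.2857 × 0.970 = 28%
- m = 60: 0.5714 × 0.826 = 47%

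**Step 3. Fixed durations, as a sensitivity check.** With onset at dosing, capture is 0% for a 10-minute reaction and 100% for one of 15 minutes or more (20 minutes or more if the check falls at the end of its window). With onset even over 0 to 120 minutes, a simulation of 1,000,000 draws gives 17% at 10 minutes, 38% at 30, 50% at 45 and 63% at 60.

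**Step 4. Meaning for one group of 36.** Assume a true rate of 10%. If a fraction c of reactions is captured, the chance that the table shows none at all is (1 − 0.10c)^36: 2% at c = 1, 16% at c = 0.5 and 40% at c = 0.25.

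**Step 5. Other routes to the data.** Section 9.6 keeps subjects under staff observation for at least 2 hours. Sections 14.1.2 and 14.1.3 schedule adverse event collection after each dose. Section 15.3 takes observed and spontaneously reported events, and section 15.3.2 scripts a general question about health problems since the last evaluation. These routes cover the interval, but none names pain or pruritus, and the plan does not pass their results into the tables of section 18.5.2.2.

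**The case against.** The strongest reply is that the endpoint is measured exactly as defined. Sections 10.1.1, 15.1 and 18.5.2.2 and Table 2 agree on the time points, all groups are rated at the same post-dose times, and the analysis is descriptive with no test attached. Asking for the worst symptom over an interval is a different measure, with its own recall error. This stands to the extent that the operative sections do not contradict one another. The mismatch is with the purpose stated in section 9.5.

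A reader might infer that the schedule misses most short reactions. The documents do not support that. With onset at dosing, missing most requires a mean duration below about 21.6 minutes. Means of 45 to 60 minutes also fit section 9.5 and leave 72% to 78% of reactions present at the first check.

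A reader might also infer that only moderate or severe local reactions can become adverse events. Section 15.1 sets an automatic reporting rule for those grades and does not bar others. A mild reaction that is observed, volunteered or given in answer to the section 15.3.2 question can be logged, and a moderate or severe one between checks has a route into the adverse event endpoint.

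Finally, a reader might infer that the Endocine dose-response will be distorted. Equal 50% incidence with mean durations of 15 and 30 minutes would read as 0.5 × 37% = 18% against 0.5 × 61% = 30% at the first check, but this is hypothetical. Section 9.5 reports a slightly higher incidence at 2% and says nothing of duration differing by concentration. A longer-lasting reaction would in any case be a real tolerability difference.

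**Conclusion.** The concern holds as a possible under-count of unknown size. In-clinic pain and pruritus that resolve before the first check, or arise and end between the checks, can be scored none in the administration-site tables. Under onset at dosing and exponential duration, capture at 15 minutes runs from 22% (mean 10 minutes) to 78% (mean 60 minutes). Those durations are assumptions, and the documents do not allow the range to be narrowed. Because adverse event collection covers the same 2 hours, the main loss is mild, brief symptoms. An effect on group comparisons is possible only if duration differs by formulation. No error rate, power or sample size is involved. The change is worth making because it is cheap and because symptoms not asked about on the day cannot be reliably recovered later.

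**What to change.** **Section 15.1.** Keep the current-status ratings. At the 15-minute check, also ask each subject for the worst pain and worst pruritus since dosing. At the 120-minute check, ask for the worst of each since the 15-minute check. Use the same four grades.

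**Section 18.5.2.2.** Tabulate, by group and vaccination occasion, the number and percentage of subjects with any post-dose pain or pruritus and their worst grade. Keep the tables by time point to show the time course.

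**Synopsis and section 10.1.1.** Align the endpoint wording with these ratings.

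Evaluator-rated swelling and redness stay as scheduled. They share the same check times, but subject recall cannot supply an inspection finding.

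**Cost.** Two symptoms at two checks make four extra answers per dosing visit, plus the matching eCRF fields and one table. No visit or staff is added. The downsides are recall over up to about 105 minutes (120 − 15) and somewhat higher reported frequencies.
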